3.4 Study Time Frame

The duration of the study for each participant will be 34 weeks: 2 weeks before randomization as eligibility screening and baseline assessment, 8 weeks of treatment period, and 24 weeks of follow up period after the cessation of treatment (Figure 1. Study Design).

[figure not shown]

Figure 1. Study Design

There will be twelve clinical visits:

Visit 1 will be scheduled during weeks -1 and -2 as eligibility screening and baseline assessment;

Visit 2 will be scheduled for baseline assessment and randomization;

Visits 3-10 (20 sessions of treatments) will be scheduled for the 8-week treatment period;

Visits 11 and 12 will be scheduled at weeks 20 and 32, respectively, during 24-week follow-up period.

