5.1.2 Secondary Outcomes

(1) Proportion of responders during weeks 1–7, and at week 20.

The NIH-CPSI will be assessed once a week during treatment, and at week 20 and week 32. The responder is defined as who has a decline of 6 or more than 6-point from baseline measured by using the NIH-CPSI.

(2) The change from baseline in NIH-CPSI total score during weeks 1–8, at week 20, and at week 32.

(3) The change from baseline in NIH-CPSI subscales (pain, urinary symptoms and QoL) during weeks 1–8, at week 20, and at week 32.

(4) The change from baseline in IPSS at week 4, week 8, week 20, and week 32.

IPSS is a valid, reliable and sensitive measure for patients with lower urinary tract symptoms (LUTS); it is widely used in clinical practice and research to determine the severity of LUTS, including incomplete bladder emptying, frequency of urination, intermittency, urgency, weak urine stream, straining and nocturia^{30, 31}. Each of the questions is rated from 0 (not at all) to 5 (almost always); severity of LUTS can be graded as mild (0–7), moderate (8–19) or severe (20–35). IPSS will be assessed at the end of the 4th, 8th, 20th, and 32nd week.

(5) The change from baseline in HADS at week 8, week 20, and week 32.

HADS will be assessed at the end of the week 8, week 20, and week 32. HADS is made up of 7 items for the assessment of depression and anxiety; the completion of this scale usually requires 2–5 minutes³².

(6) The change from baseline in IIEF-5 at week 8, week 20, and week 32.

Chinese version IIEF-5 will be assessed at the end of the week 8, week 20, and week 32. The IIEF-5 consists of 15 items in 5 domains with a total score ranging from 5 to 25 (mild ED, 12–21; moderate ED, 8–11; severe ED, 5–7); it is a psychometrically valid and reliable instrument with high sensitivity and specificity for detecting treatment effects in patients with ED of a broad spectrum of aetiology³³.

(7) The change from baseline in EQ-5D-5L at week 8, week 20, and week 32.

The EQ-5D-5L will be assessed at the end of week 8, week 20, and week 32. The EQ-5D-5L is a generic instrument designed for self-completion and postal surveys; it is well-established and suitable for evaluation of QoL in participants with CP/CPPS³⁴.

(8) The proportions of participants in each response category of the Global Response Assessment (GRA) at week 4, week 8, week 20, and week 32.

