The proportions of participants in each response category of the GRA in the two groups after treatment will be measured at the end of the week 4, week 8, week 20, and week 32. GRA consists of 7 response categories: markedly worsened, moderately worsened, slightly worsened, no change, slightly improved,

moderately improved, and markedly improved. We will identify a participant who reports “moderate” or “marked improvement” as a responder³⁵.

(9) The change for peak and average urinary flow rates from baseline at weeks 8 and 32.

Peak and average urinary flow rates will be measured at weeks 8 and 32.

(10) Expectation assessment at baseline

Expectation assessment will be assessed at baseline, which includes two brief questions to investigate whether patients are confident that acupuncture treatment will help their CP/CPPS: “In general, is acupuncture effective for controlling the illness?”, “Do you think acupuncture will be helpful to improve your CP/CPPS symptoms?” For each question, participants could choose “Yes”, “No” or “Unclear” as the answer.

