6.3.3 Analyses for Primary Outcome

Primary outcome analysis will be conducted with a logistic generalized linear mixed model (GLMM) for repeated measures. Responder or non-responder at each scheduled post-baseline visit (end of treatment, and 20 and 24 weeks after treatment) is the dependent variable. Subjects who discontinue without providing the NIH-CPSI score will be considered as non-responders. The logistic GLMM is fitted using the logit link and the binomial distribution. The model will include the baseline NIH-CPSI total score as a fixed-effect covariate, with treatment group (acupuncture and sham acupuncture), visit and treatment \times visit interaction as fixed-effect categorical factors. The interaction will remain in the model regardless of significance. Treatment group comparisons at each visit will be estimated by differences between least squares means from the treatment \times visit interaction, and will be presented as odds ratios with accompanying *p* values and 95% CIs. The predicted probability of response at each visit will also be presented. Such models provide fairly robust results for treatment comparisons when longitudinal binary responses are missing, with an assumption that data are missing at random(MAR), according to reported values³⁶.

Sensitivity Analyses for the Primary Outcome

Because the MAR assumption cannot be verified using the data, the sensitivity of inferences to departures from the MAR assumption should be tested³⁷. A straightforward sensitivity analysis for the MAR assumption in multiple imputation is based on the control-based pattern imputation model under the MNAR assumption by using the SAS procedure Proc MI process. Therefore, mixed-effect model under MNAR assumption will be used. 6.3.4 Analyses for Secondary Outcome

Efficacy analyses for all secondary outcomes will be performed in the ITT population, without imputation of missing data.

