Continuous data will be described with the average, standard deviation, median, minimum value, and maximum value, whereas categorical data will be represented by percentages as appropriate. Changes from baseline in the NIH-CPSI total score will be analyzed using linear mixed-effects model. The model will include the observed change from baseline score at each assessment point as the dependent variable; the baseline value, treatment group (acupuncture and sham acupuncture), visit and treatment \times visit interaction as fixed effects. Treatment group comparisons at each visit will be estimated by differences between least squares means from the treatment \times visit interaction, with accompanying *p* values and 95% CIs. Log-transformation may be applied in the case of serious violations of the model assumptions (normality and constant variance of the residuals). If not appropriate, the Wilcoxon rank-sum test will be used. The effect of the treatment will be estimated by the difference (or ratio, in the case of log-transformation) between treatments and will be presented along with its associated 95% CI. The same

approach will be used in other longitudinal continuous outcomes such as NIH-CPSI subscale scores (pain, urinary symptoms, and QoL).

Other categorical data or ordinal data will be compared between groups using the Wilcoxon rank-sum test, chi-square test or Fisher's exact test, as appropriate. The James and Bang blinding indices will be used to assess the success of blinding. The James blinding index is a variation on the statistic in which 1 represents perfect blinding. The Bang blinding index for each group represents the proportion of participants making a correct treatment guess beyond chance; 0 represents perfect blinding, a positive index indicates a correct guess, and a negative index indicates a guess in the opposite direction.

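### The NIH-CPSI responder outcome has two missing-data rules, one for weeks 8 and 32 and another for weeks 1–7 and 20, and week 20 very probably gets two estimates

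*Combined protocol and SAP*

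**What the plan says.** **Primary rule.** SAP 6.3.3 fits a repeated-measures logistic mixed model to responder status and states: "Subjects who discontinue without providing the NIH-CPSI score will be considered as non-responders". The visits are given as: "Responder or non-responder at each scheduled post-baseline visit (end of treatment, and 20 and 24 weeks after treatment) is the dependent variable". Results are reported visit by visit as odds ratios with p values and confidence intervals, together with predicted probabilities of response.

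**Secondary rule.** SAP 6.3.4, whose heading runs on from the end of the 6.3.3 text, states: "Efficacy analyses for all secondary outcomes will be performed in the ITT population, without imputation of missing data". The first secondary outcome in SAP 5.1.2 is "Proportion of responders during weeks 1–7, and at week 20", defined by the same decline of at least 6 points in NIH-CPSI as the co-primary outcomes in SAP 5.1.1. No sentence carries the 6.3.3 rule over to it. In 6.3.4 a mixed model is named for continuous outcomes only. For the rest: "Other categorical data or ordinal data will be compared between groups using the Wilcoxon rank-sum test, chi-square test or Fisher's exact test, as appropriate".

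**Visits.** Protocol 3.4 gives an 8-week treatment period and then: "Visits 11 and 12 will be scheduled at weeks 20 and 32, respectively, during 24-week follow-up period". The schedule tables in both documents show no other follow-up visit.

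**Analysis set and reporting.** SAP 6.2 bases all analyses on every randomised man. SAP 6.3.1 asks for a treatment difference with a 95% confidence interval for primary and secondary outcomes alike, and for the number of missing values for each variable.

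**The concern.** A man who withdraws in week 5 and gives no further score is a non-responder at weeks 8 and 32. At week 20, under 6.3.4, he has no value, and a chi-square or Fisher test on the available data leaves him out. The same binary variable thus changes its meaning between visits.

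Two things are at stake. The SAP objective stresses long-term efficacy, so readers will compare response proportions across weeks 7, 8, 20 and 32, and part of any movement between them could come from the change of rule. In addition, if week 20 is in the primary model, the SAP yields a model-based week-20 comparison under one rule and a secondary week-20 comparison under the other. Nothing says which is the reported result, so the choice could be made after both have been seen.

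**Working it through.** **Step 1. Is week 20 in the primary model?** Treatment lasts 8 weeks, so the follow-up visits fall at 20 − 8 = 12 and 32 − 8 = 24 weeks after treatment. The bracket in 6.3.3 names 20 and 24 weeks after treatment, which taken literally means weeks 8 + 20 = 28 and 8 + 24 = 32. No week-28 visit exists. Week 20 is the only scheduled visit between weeks 8 and 32, so it is the only one that the first term can mean. This is an inference from the schedule and not a statement in the SAP.

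**Step 2. The two rules side by side.**

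| NIH-CPSI responder status | Governing text | Man who discontinued without a score |
|---|---|---|
| Weeks 1–7 | 6.3.4 | Not imputed |
| Week 8 | 6.3.3 | Non-responder |
| Week 20, as secondary outcome | 6.3.4 | Not imputed |
| Week 20, as visit in the primary model (Step 1) | 6.3.3 | Non-responder |
| Week 32 | 6.3.3 | Non-responder |

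**Step 3. The plan's own figure.** Protocol 11.1 gives 63.7% v 46.7%, 90% power, two-sided alpha 0.05, a 15% increase for dropouts, and 220 per group. The usual two-proportion formula with pooled variance under the null gives 178 per group, or 190 with continuity correction. Then 190 × 1.15 = 218.5, rounded up to 219, and 190 / 0.85 = 223.5, rounded up to 224. The stated 220 reproduces. The odds ratio is (0.637/0.363) / (0.467/0.533) = 2.00, as stated. None of this is disputed.

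**Step 4. How far apart the rules can be at week 20.** Assumptions: the planning rates hold among men who report at week 20, every missing man is a discontinuer, and a fraction d is missing in an arm. The documents give only the 15% allowance; the other values of d are chosen to show the range. These are raw proportions, not output of the mixed model.

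- Without imputation: rate = p, so 63.7% v 46.7%, 17.0 points, OR 2.00, whatever d is.
- Discontinuers as non-responders: rate = p × (1 − d).
- At d = 15% in both arms: 0.637 × 0.85 = 54.1% and 0.467 × 0.85 = 39.7%. The difference is about 14.4 points, and the OR is (0.541/0.459) / (0.397/0.603) = 1.79. The denominators are 220 per arm, against 220 × 0.85 = 187 per arm without imputation.

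| Missing, acupuncture / sham | Not imputed | Discontinuers as non-responders |
|---|---|---|
| 0% / 0% | 17.0 points, OR 2.00 | 17.0 points, OR 2.00 |
| 5% / 5% | 17.0, 2.00 | 16.1, 1.92 |
| 10% / 10% | 17.0, 2.00 | 15.3, 1.85 |
| 15% / 15% | 17.0, 2.00 | 14.4, 1.79 |
| 20% / 10% | 17.0, 2.00 | 8.9, 1.43 |
| 10% / 20% | 17.0, 2.00 | 20.0, 2.25 |

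The last two rows have no source in the documents. They show only that unequal dropout can move the gap in either direction.

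**The case against.** The strongest reply is that the text is ambiguous and not contradictory. The tests in 6.3.4 are for other categorical data, so the 6.3.3 model might be meant to supply the week-20 responder result. Counting a discontinuer as a non-responder might also be read as part of the responder definition and not as imputation. Both readings are fair, but neither is written down. Week-20 response is listed as a secondary outcome, and the no-imputation sentence covers all secondary outcomes. Weeks 1–7 are outside the three visits in the bracket, so the first reading does not reach them.

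A simpler missing-data rule for secondary outcomes is a common choice, and the missing counts required by 6.3.1 make the denominators visible. That is true, but disclosure does not settle which of two week-20 results is the planned one.

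Several stronger readings are tempting, and the documents do not support them:

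- **Weeks 8 and 32 use every randomised man.** The 6.3.3 rule covers only men who discontinue without a score. Other gaps are left to the model under a missing-at-random assumption, and Protocol 10.3 keeps less compliant men in follow-up.
- **The response curve will zigzag.** That would require the secondary week-20 percentage to be placed between two primary results, and no section plans such a curve. The week 8 to week 32 comparison is under one rule throughout.
- **The no-imputation result is the biased one.** If missing men would have responded like those who report, the 17.0 points would be right and the other figures distorted. The arithmetic does not decide this.
- **The Global Response Assessment must follow the same rule.** SAP 5.1.2 says "We will identify a participant who reports “moderate” or “marked improvement” as a responder", but this is a separate instrument that never enters the primary model. No second estimate arises, and its missing-data rule is a matter of preference.

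**Conclusion.** The point holds as an inconsistency in the SAP. The NIH-CPSI responder variable has one missing-data rule at weeks 8 and 32 and another at weeks 1–7 and 20, with no statement reconciling them. That week 20 has two estimates is very probable and not certain. It rests on reading the first follow-up term in the 6.3.3 bracket as the only scheduled visit that fits. If week 20 were not in the model, the two-estimate point would fall and the difference of rules between visits would remain.

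At the plan's own 15% allowance in both arms, and with the planning rates taken as the rates among men who report, the two week-20 differences are 17.0 and about 14.4 points (OR 2.00 and 1.79). The gap depends on dropout and disappears without it. The co-primary results and the sample size do not change. This is an inexpensive correction worth making, not a threat to the primary conclusion.

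**What to change.** 1. In SAP 6.3.3, correct the visit list to weeks 8, 20 and 32, that is, end of treatment and 12 and 24 weeks after treatment.
2. Apply the 6.3.3 discontinuation rule to the NIH-CPSI responder outcome at every visit, including weeks 1–7 and 20. State how intermittently missing scores are treated, and treat them in the same way at every visit.
3. State that the week-20 responder result comes from the 6.3.3 model only.
4. In 6.3.4, exempt the NIH-CPSI responder outcomes from the no-imputation sentence, and report observed-case rates in a table labelled as supplementary. The Global Response Assessment may keep its own rule, provided that the SAP states it.

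The cost is a few sentences and no new data. Protocol 11.2 has the final SAP approved before database lock and code breaking, so the choice can be made without sight of results. The one downside is that secondary response rates will look lower when men discontinue.

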8.1. Outcomes Measurements

8.1.1 Primary Outcomes

The two co-primary outcomes include the proportions of responders at week 8 and week 32. The

responder is defined as a participant with a decline of 6 points or more from baseline in the total score of the Chinese version NIH-CPSI. As a validated, self-reported questionnaire, NIH-CPSI is widely used to assess CP/CPPS symptoms^{29,30}. NIH-CPSI consists of 9 items divided into 3 discrete domains: pain (0–21 points), urinary symptoms (0–10 points) and QoL (0–12 points), with a total score of 0–43 points (a higher score indicates worse symptoms). A decline of at least 6 points in NIH-CPSI has been identified as the minimal clinically important difference (MCID)²⁵.

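### The log-transformation fallback for secondary outcomes is attached to a change score, where it cannot be computed for all men, and the rank test that follows it discards the baseline adjustment and the joint use of visits

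*Combined protocol and SAP*

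**What the plan says.** SAP section 6.3.4 (Analyses for Secondary Outcome) sets out the analysis of change in NIH-CPSI total score.

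- **Dependent variable:** "The model will include the observed change from baseline score at each assessment point as the dependent variable".
- **Fixed effects:** "the baseline value, treatment group (acupuncture and sham acupuncture), visit and treatment"-by-visit interaction.
- **First fallback:** "Log-transformation may be applied in the case of serious violations of the model assumptions", these assumptions being normality and constant variance of the residuals.
- **Second fallback:** "If not appropriate, the Wilcoxon rank-sum test will be used".
- **Effect measure:** "The effect of the treatment will be estimated by the difference (or ratio, in the case of log-transformation) between treatments", with a 95% confidence interval. SAP section 6.3.1 likewise promises treatment differences with 95% intervals for secondary outcomes.
- **Scope:** the same "approach will be used in other longitudinal continuous outcomes such as NIH-CPSI subscale scores (pain, urinary symptoms, and QoL").

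Section 6.3.4 also states that missing values are not imputed for secondary outcomes. It does not define the sign of the change, name a constant to add before taking logs, or say that the raw score would be logged instead.

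Protocol section 8.1.1 gives the direction of the scale: "a higher score indicates worse symptoms". It also gives the threshold for response: "responder is defined as a participant with a decline of 6 points or more from baseline in the total score".

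**The concern.** A logarithm exists only for values above zero. A change score takes values on both sides of zero as well as zero itself, so the first fallback cannot be carried out on the stated variable. A ratio between treatments has no clear meaning for it either.

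That leaves the rank-sum test as the only workable fallback. A two-sample rank test has no baseline covariate, visit term, interaction or within-subject correlation, so it must be run separately at each visit on the men observed then. If the residuals look poor, the plan would therefore give up the useful features of its mixed model and would have no named estimator for the difference and interval it has promised. At stake is the continuous counterpart of the responder endpoint, together with the subscales and the other longitudinal continuous outcomes.

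**Working it through.** **Planning rates.** Protocol section 11.1 gives responder rates of 63.7% and 46.7% and an odds ratio of 2.0. Check: (0.637/0.363) / (0.467/0.533) = 1.755 / 0.876 = 2.00. At two-sided 0.05 and 90% power, a continuity-corrected two-proportion calculation gives 190 per group. Then 190 × 1.15 = 219 and 190/0.85 = 224, both close to the stated 220. The rates are used below as the plan's own figures; none of them is disputed.

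**Range of the dependent variable.** The total score runs from 0 to 43 and entry requires at least 15 (protocol sections 8.1.1 and 4.2). Post minus baseline therefore runs from 0 − 43 = −43 to 43 − 15 = +28. Baseline minus post runs from −28 to +43. Both ranges include zero and negative values.

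**Where the log fails.**

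| Definition of change | Log undefined for | Bound from the planning rates |
|---|---|---|
| Post minus baseline | Every improved and every unchanged man | At least 63.7% acupuncture, 46.7% sham |
| Baseline minus post | Every unchanged and every worsened man | At most 36.3% acupuncture, 53.3% sham |

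The first row is a floor. Every responder has a change of −6 or lower, and men who improve by 1 to 5 points or do not change add to the count. Taking all 220 per group as observed, the floor is 220 × 0.637 = 140 men and 220 × 0.467 = 103 men. The second row is a ceiling: non-responders are 100 − 63.7 = 36.3% and 100 − 46.7 = 53.3%, and those who improved by 1 to 5 points would still be computable. These bounds apply to the primary time points, weeks 8 and 32. The documents give no rates for weeks 1 to 7 or week 20.

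**Would a shift constant rescue it?** With a minimum of −43, an integer constant must be at least 44. Take two changes of −8 and −5, chosen for illustration. With 44 added, the ratio is 36/39 = 0.92. With 100 added, it is 92/95 = 0.97. The same three-point difference yields a different effect depending on an arbitrary constant, and the SAP names none.

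**Cost of the Wilcoxon step.** In the linear-model approximation, dropping a baseline covariate that has correlation r with the change leaves a relative efficiency of 1 − r². The documents give no r. For an assumed r of 0.3 this is 1 − 0.09 = 0.91; for an assumed r of 0.6 it is 1 − 0.36 = 0.64. The rank-sum test also returns a p-value, not a difference with an interval, and no companion estimator is specified.

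**The case against.** The wording is permissive. The log may be applied, and if it is unsuitable the Wilcoxon test follows. A reader might infer that the plan would delete the men who improved and compare only those who got worse. The documents do not support that. Nothing tells the analyst to drop anyone, and a log that is undefined for many men is an obvious reason to move to the next step. The sign of the change is also undefined, so the claim that the log fails for responders holds only for post minus baseline. What stands under both signs is that it cannot be computed for everyone.

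A reader might also fit a normal distribution to the planning rates. With post minus baseline and an assumed SD of 5 to 10, about 83–94% of acupuncture values and 70–87% of sham values would be zero or negative. These figures should not carry weight: no SD is given in the documents, and the fallback is triggered precisely when normality or constant variance fails.

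The reference to a ratio suggests that the authors may have had the raw score in mind. That is plausible, but the text does not say so, and raw totals and subscales can themselves be 0.

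A visit-wise rank test is a valid randomised comparison when data are complete, so calling the result wrong would go too far. The loss is in precision, in the handling of missing visits and in the missing effect estimate. Nor is the choice of method unguarded. The order of the fallbacks is fixed in advance, the SAP is to be final before the code is broken (protocol section 11.2), and the statisticians are blinded (protocol section 6.2). No threshold for a serious departure is given, however.

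**Conclusion.** The point holds as a defect in a conditional rule for the secondary continuous outcomes. The log step and its ratio cannot be executed for all participants on the variable the SAP names, whichever way change is signed. This follows from the range of the scale and needs no distributional assumption. The floor of 63.7% and 46.7% rests on the post-minus-baseline convention and on the planning rates at the primary time points.

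The practical consequence is a move to a visit-by-visit Wilcoxon test with the losses described above. Their size depends on a baseline-to-change correlation that the documents do not give. The main mixed model is sound, and the co-primary responder analysis and the sample size are not touched.

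**What to change.** In SAP section 6.3.4:

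1. Delete the log-transformation of the change score and the wording about a ratio.
2. Keep the linear mixed-effects model as the analysis of every longitudinal continuous outcome, with robust (sandwich) standard errors if the residuals are non-normal or heteroscedastic. The effect is then always a difference in least squares means with its 95% confidence interval.
3. Keep the Wilcoxon rank-sum test only as a labelled sensitivity analysis, not as a replacement.

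This is a change of wording and needs no new data. The only thing given up is a data-driven fallback, which matters little with a planned 220 men per group.

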8.1.2 Secondary Outcomes

Secondary outcomes include:

- (1) Proportion of responders during weeks 1-7, and at week 20.

The NIH-CPSI will be assessed once a week during treatment, and at week 20 and week 32. The responder is defined as who has a decline of 6 or more than 6-point from baseline measured by using the NIH-CPSI.

- (2) The change from baseline in NIH-CPSI total score during weeks 1-8, at week 20, and at week 32.
- (3) The change from baseline in NIH-CPSI subscales (pain, urinary symptoms and QoL) during weeks 1-8, at week 20, and at week 32.

- (4) The change from baseline in IPSS at week 4, week 8, week 20, and week 32.

IPSS is a valid, reliable and sensitive measure for patients with lower urinary tract symptoms (LUTS); it is widely used in clinical practice and research to determine the severity of LUTS, including incomplete bladder emptying, frequency of urination, intermittency, urgency, weak urine stream, straining and nocturia^{31,32}. Each of the questions is rated from 0 (not at all) to 5 (almost always); severity of LUTS can be graded as mild (0–7), moderate (8–19) or severe (20–35). IPSS will be assessed at the end of the 4th, 8th, 20th, and 32nd week.

- (5) The change from baseline in HADS at week 8, week 20, and week 32.

HADS will be assessed at the end of the week 8, week 20, and week 32. HADS is made up of 7 items for the assessment of depression and anxiety; the completion of this scale usually requires 2–5 minutes³³.

- (6) The change from baseline in IIEF-5 at week 8, week 20, and week 32.

Chinese version IIEF-5 will be assessed at the end of the week 8, week 20, and week 32. The IIEF-5 consists of 15 items in 5 domains with a total score ranging from 5 to 25 (mild ED, 12–21; moderate ED, 8–11; severe ED, 5–7); it is a psychometrically valid and reliable instrument with high sensitivity and specificity for detecting treatment effects in patients with ED of a broad spectrum of aetiology³⁴.

- (7) The change from baseline in EQ-5D-5L at week 8, week 20, and week 32.

The EQ-5D-5L will be assessed at the end of week 8, week 20, and week 32. The EQ-5D-5L is a generic instrument designed for self-completion and postal surveys; it is well-established and suitable for evaluation of QoL in participants with CP/CPPS³⁵.

- (8) The proportions of participants in each response category of the Global Response Assessment (GRA) at week 4, week 8, week 20, and week 32.

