11.1 Sample Size Calculations

Sample-size calculations were based on 90% power to detect a difference of 17% between response rates in the two groups (63.7% in the acupuncture group compared with 46.7% in the control group) for the primary outcome, defined as a decline of 6 or more points in the NIH-CPSI total score²¹. These values are equivalent to an odds ratio of 2.0. On the basis of a two-sided alpha level of 0.05, we calculated that a sample of 440 participants will be required (220 in each group). This proposed sample size includes a 15% increase to account for dropouts. To control for type I error, the two time points in the primary outcomes will have to be positive in order for the trial to prove the efficacy of acupuncture.

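### On the most natural reading of the SAP, responder status at weeks 1–7 is compared without baseline adjustment, although the later responder analysis and the weekly change scores are adjusted; the cost is modest and the repair is cheap

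*Combined protocol and SAP*

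**What the plan says.** Protocol 8.1.2 and SAP 5.1.2 list as secondary outcome (1): "Proportion of responders during weeks 1-7, and at week 20". The definition is that of the co-primary outcomes at weeks 8 and 32, a fall of at least 6 points in NIH-CPSI total score.

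Three SAP provisions bear on its analysis:

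- **SAP 6.3.3 (primary).** The dependent variable of the logistic mixed model is "Responder or non-responder at each scheduled post-baseline visit (end of treatment, and 20 and 24 weeks after treatment"). On covariates: "The model will include the baseline NIH-CPSI total score as a fixed-effect covariate". Results are odds ratios, with predicted response probabilities at each visit.
- **SAP 6.3.4 (secondary).** NIH-CPSI total and subscale changes get a linear mixed model that includes the baseline value. For the rest: "Other categorical data or ordinal data will be compared between groups using the Wilcoxon rank-sum test, chi-square test" or Fisher's exact test. No sentence names responders at weeks 1–7.
- **SAP 6.3.1.** Primary and secondary outcomes alike are to be reported as estimated treatment differences with 95% CIs.

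**The concern.** Baseline bears directly on this variable because response is an absolute fall. A man who enters at the minimum score of 15 must lose 6/15 = 40% of it; a man at 30 must lose 6/30 = 20%. The sponsor already treats baseline as relevant by adjusting for it in 6.3.3 and in the change-score model. Dropping it for the same variable in weeks 1–7 has no stated reason.

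Three things are at stake:

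- some power in the weeks that show when response begins, where differences may be smaller than the 17 points the trial is sized for;
- a chance baseline difference between arms would go uncorrected through week 7 and be corrected afterwards;
- the responder course would join unadjusted comparisons to model-based conditional odds ratios, so an apparent change at week 8 could partly reflect the change of method.

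**Working it through.** **1. Which rule reaches weeks 1–7?** Treatment ends at week 8. Protocol 3.4 schedules follow-up at weeks 20 and 32, which are 20 − 8 = 12 and 32 − 8 = 24 weeks after treatment. The bracket in 6.3.3 gives 20 and 24 weeks after treatment; the first would be week 8 + 20 = 28, when there is no visit. The likely intention is weeks 8, 20 and 32, but that is an inference. Two readings follow:

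- the bracket defines the model's visits, so weeks 1–7 fall to the 6.3.4 rule for other categorical data;
- the words before the bracket govern, and since Protocol 8.2.3 makes Visits 3–10 weekly scheduled visits, weeks 1–7 are already in the adjusted model.

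The first is more natural, because the bracket enumerates the visits and the model sits under the primary outcome.

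**2. The plan's own figures** (Protocol 11.1). Inputs: power of 90% for a 17-point gap; assumed response of "63.7% in the acupuncture group compared with 46.7% in the control group"; a two-sided 5% level; 220 per group including 15% for dropouts.

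- Odds ratio: (0.637/0.363)/(0.467/0.533) = 2.003, which agrees with "These values are equivalent to an odds ratio of 2.0".
- Two-proportion formula, pooled variance: 178 per group, or 190 with continuity correction. 190 × 1.15 = 218.5, so 219 (438 in total), against the stated 220 (440). The figure reproduces.
- Analysed per arm after 15% loss: 220 × 0.85 = 187.

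**3. Power, risk-difference approximation.** Power = Φ[(d√n − 1.96√(2q(1 − q))) / √(p₁(1 − p₁) + p₂(1 − p₂))], with q the mean of the two rates. At n = 187, d = 0.17: (2.325 − 1.378)/0.693 = 1.37, so 91.4%. Adjustment replaces n by n/(1 − r²), where r is the correlation of baseline with the binary responder variable. The documents do not give r; the range is assumed.

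| r | 17-point difference | 10-point difference (assumed) |
|---|---|---|
| 0 | 91.4% | 49.0% |
| 0.1 | 91.7% | 49.4% |
| 0.2 | 92.4% | 50.6% |
| 0.3 | 93.7% | 52.7% |
| 0.4 | 95.3% | 56.0% |

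**4. Power, simulation of chi-square against baseline-adjusted logistic regression at one visit.** Here the assumed quantity is the correlation of baseline with the size of the decline; 0.5 on that scale is about 0.40 with the responder variable. Settings: 187 per arm, sham response 46.7%, 2,000 trials each, baseline truncated at 15 or more with mean about 27.5 and SD about 6.4, decline SD 7 (distributions assumed).

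| Correlation with decline | 17 points | 14 points | 12 points |
|---|---|---|---|
| 0.3 | 92.0 → 92.8% | 79.7 → 80.0% | 65.2 → 66.6% |
| 0.4 | 92.4 → 94.0% | 78.5 → 81.6% | 65.2 → 69.2% |
| 0.5 | 92.2 → 95.8% | 80.0 → 85.3% | 65.8 → 72.6% |

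The 46.7% rate may be too high for early weeks. At lower assumed rates (4,000 runs), the gain at correlations 0.3–0.4, and then at 0.5, was 1–2.5 and 4 points for 10% vs 17%; 2–4 and 6.5 for 20% vs 30%; 3–5 and 8 for 30% vs 42%. At a correlation of 0.2 the gain is about 0–1 point. Across settings, roughly 2–6 points at 0.3–0.5 is a fair summary; single settings run from under 1 to 8.

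**5. Odds-ratio scale.** At r of about 0.2, 0.3 and 0.4, adjustment moves an odds ratio of 2.00 to 2.06, 2.16 and 2.32, and the SE of its log from 0.212 to 0.217, 0.225 and 0.236. The interval does not narrow. Power rises because the estimate moves further from 1: ln 2.00/0.212 = 3.27 against ln 2.32/0.236 = 3.57. A subject random intercept adds to the shift: with an assumed SD of 1 or 2, a marginal odds ratio of 2.0 corresponds to a conditional 2.3 or 3.1.

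**6. Chance imbalance.** With responder SD about 0.5, a one-standard-error baseline difference shifts the unadjusted responder difference by r × 0.5 × √(2/187): about 1.0, 1.6 and 2.1 percentage points at r = 0.2, 0.3 and 0.4.

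**The case against.** The strongest reply is that the SAP nowhere assigns chi-square or Fisher tests to responders at weeks 1–7; a reader might infer that it prescribes them, but the text reaches them only by default and can be read to put those weeks in the adjusted model. This stands, and it is why the point is about a default and an unclear visit list. The ambiguity is no defence of the plan, since one sentence settles both.

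A reader might also infer a large loss. At a correlation of 0.5 with the binary responder variable, the approximation in step 3 gives 91% to 97% for 17 points, 78% to 88% for 14 and 64% to 77% for 12. By the conversion in step 4 that needs about 0.5 × 0.5/0.40 = 0.63 with the decline, and nothing in the documents supports so high a value.

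The early course is also covered by the baseline-adjusted change-score model for weeks 1–8, which is more informative than the responder split. That is correct and limits the consequence.

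Finally, a common proportion scale is partly available, because 6.3.3 presents predicted probabilities and 6.3.1 asks for treatment differences. So a spurious step at week 8 is possible, not shown. The missing-data rules could produce one too: men who discontinue without a score count as non-responders in the primary analysis, while secondary outcomes are not imputed. With an assumed 15% missing per arm, observed rates of 63.7% and 46.7% become 0.85 × 63.7 = 54.1% and 0.85 × 46.7 = 39.7%, and the difference falls from 17.0 to 14.5 points.

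**Conclusion.** The concern holds as a minor, inexpensive improvement. It rests on taking the bracket in 6.3.3 as the model's visit list, and its size on an assumed baseline–decline correlation.

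The documents do not support reading this as a threat to the trial's result. Unadjusted tests are valid under randomisation, the outcome is secondary with no multiplicity control claimed, and the co-primary tests, type I error and sample size are untouched. Nor do they support a claim of tighter odds-ratio intervals: the benefit is power, plus protection against chance imbalance and a consistent scale over time.

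**What to change.** Before database lock and unblinding:

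- In SAP 6.3.4, state that responder status at weeks 1–7 is analysed with a separate logistic model for repeated measures containing baseline NIH-CPSI total score, treatment, visit and their interaction, with a baseline-adjusted logistic regression at each visit as fallback.
- At every visit, report the baseline-standardised risk difference with 95% CI beside the odds ratio. This meets 6.3.1 and puts early and late results on one scale.
- In 6.3.3, correct the bracket to weeks 8, 20 and 32, so that the week 20 result comes from the primary model.
- State which missing-data rule applies to responder status at weeks 1–7 and 20.

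The cost is a few sentences and one further model run, with no new data, visits or participants. The small downside is possible non-convergence in early weeks with few responders, which the fallback is meant to cover. Apart from the corrected visit list, the primary model stays as it is.
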